## **14.0 BIOSTATISTICS**

This primary objective of this study is to estimate the response rates (CR + PR) to treatment following hepatic arterial embolization of hepatocellular cancer (HCC) using microscopic beads + Doxorubicin and beads alone by conventional RECIST criteria. With 50 patients in each arm response rates can be estimated to within +/- 14%. Patients will be randomly assigned to one the two treatment arms. A two-arm study was deemed necessary because there was not sufficient preliminary data on the control arm to design a single-arm study with historical controls. This is not a study where the goal is to test a hypothesis, rather the emphasis is on the estimation of response rates in the two arms. For this reason the sample size justification is provided in terms of the precision (half length of the asymptotic confidence interval) of these estimates instead of a power calculation. This is in the same spirit with most randomized Phase II trials of chemotherapeutic agents.

Randomization will be performed using the Clinical Research Database (CRDB), the central computing facility for clinical research at MSKCC. This system will generate a treatment assignment using the method of permuted blocks, at the time the patient is registered. Due to the nature of the treatment, the interventional radiologist will not be blinded but the radiologists assessing response to treatment will be blinded to treatment assignment.

One of the secondary objectives is to quantify the amount of necrosis in the two treatment arms and correlate this with conventional RECIST response as well as time to progression. With 50 patients in each arm, percent necrosis can be estimated to within +/- 14% of its standard deviation. Using 50% necrosis as threshold we plan to evaluate the degree of agreement between RECIST and necrosis response using Cohen's kappa and McNemar's test.

Another secondary objective is to establish whether the use of the doxorubicin eluting beads might prolong time to progression (TTP), or survival, and if initial imaging response to treatment, as manifested by necrosis, correlates with either endpoint. This aim relates to analysis with censored outcomes (time-to-progression and survival time). We will use the Kaplan-Meier method to estimate the survival probabilities and we will use the log-rank test to compare groups. With 50 patients in each arm, we will have approximately 80% power to detect a hazard ratio of 3, assuming a median follow-up of 3 years (i.e., about half of the patients expiring) and controlling the Type I error rate at 5%. A hazard ratio of 3 corresponds to improving the median survival by three-fold or improving two-year survival by approximately 20%. We do not anticipate a survival difference of this magnitude so this aim will primarily serve to obtain preliminary data to plan a future definitive trial.

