## 1.0 PROTOCOL SUMMARY AND/OR SCHEMA

Purpose:	The objective of this study is to evaluate hepatic arterial embolization for hepatocellular cancer using microscopic beads and the same microscopic beads loaded with doxorubicin.
Study design:	Single center, single blind, prospective, randomized phase II controlled, to be conducted without crossover with patients recruited over a 2 year period
Study agents:	Biocompatibles LC Bead ( Beads + doxorubicin ), 100-300 microns, 150 mg doxorubicin per procedure with additional 100-300 micron and larger size beads (Bead Block) as necessary to achieve stasis  Bead Block ( Beads ) microsphere, 100-300 micron with additional larger size beads as necessary to achieve stasis
Limitations of Study	LC Bead and Bead Block are both tinted blue. Because doxorubicin is red, the addition of doxorubicin to the embolization microspheres will change the color of the spheres to some degree, and thus it may be possible for the interventional radiologist performing the embolization to differentiate between the two embolics. All other participants performing image and data analysis will be blinded.
Enrollment:	100 patients will be enrolled, 50 in each study arm
Clinical site:	Memorial Sloan-Kettering Cancer Center, NY, NY
Primary endpoint:	Response to treatment by RECIST criteria
Secondary endpoints:	

• Tumor necrosis

• Toxicity

• Time to progression

• Survival

Safety endpoint:	The safety endpoint will be treatment related Serious Adverse Event (SAE) rate, defined by SAE occurring within 30 days of a procedure. SAE is defined as a grade 3 or 4 adverse event using the Common Terminology Criteria for Adverse Events (CTCAE) 3.0.
Primary analysis:	Intent-to-treat analysis
Secondary Analysis:	Per protocol analysis and treated population analysis
Principle Investigator:	[name]

Member  
Department of Radiology  
Memorial Sloan-Kettering Cancer Center  
[name]  
[name]

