## 2.0 OBJECTIVES AND SCIENTIFIC AIMS

### **Primary Objective**

In this study one group of patients with hepatocellular cancer (HCC) will undergo hepatic arterial embolization using microscopic beads + doxorubicin and another group with the microscopic beads alone. Response to treatment will be determined in each group by conventional RECIST criteria. Since there is no historical data on imaging response to treatment for either group, the

study will be randomized. The primary objective will be to estimate the response rate in the two arms.

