A microscopic bead has been developed that can be used as an embolic agent alone, or loaded with doxorubicin to deliver high concentration of the drug to a target tumor within the liver while limiting systemic exposure. Before this agent that is much more expensive than conventional embolic material comes into widespread use, it would be valuable to assess its effectiveness. Since the agent is itself an embolic and can be used without loading doxorubicin, the opportunity exists to determine to what extent the addition of chemotherapy enhances the effect of embolization alone. Although survival is clearly the most important endpoint in evaluating treatments for HCC, survival studies require several years of follow-up in these patients, whereas preliminary data regarding response to treatment can be obtained using imaging. Traditionally, Response Evaluation Criteria In Solid Tumors (RECIST) have been used to evaluate response to treatment, and will be used as a primary endpoint in this study. These criteria are based on the product of bi-dimensional orthogonal measurements of a treated lesion, and do not take into account the degree of tumor necrosis resulting from treatment. The Barcelona-2000 EASL conference [Bruix J, et al 2001] concluded that tumor necrosis is an important indicator of

response to treatment for HCC, and recommended that changes in viable tumor area, rather than overall tumor area, be used to assess response. RECIST criteria have been found to be insensitive when used to evaluate other tumors that develop significant necrosis in response to treatment, such as the response of GIST tumors to Imatinib [Benjamin RS, et al 2006]. In this study, % tumor necrosis will serve as a secondary endpoint. Tumor necrosis will be quantified on contrast enhanced CT scans using an automated volumetric method, and the relationship of tumor necrosis to response as measured by RECIST criteria will be determined. These 2 measures of response to treatment will be correlated with TTP and survival in an attempt to establish the utility of one or the other as a surrogate outcome marker.

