### **Measurement of Treatment Response**

Contrast enhanced CT and MRI are the best currently available methods of evaluating response to treatment for HCC, and the most reproducible means of measuring target lesions and assessing necrosis. Triple phase contrast enhanced CT scans will be performed 2-3 weeks after the first complete treatment. Patients will be grouped according to RECIST criteria; however the volumetric assessment will use a continuous scale of percent tumor necrosis.

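### The objective asks for correlation of necrosis with RECIST response, but the only named methods are agreement statistics at a 50% cut, where kappa is capped low if RECIST response is much the rarer

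*Combined protocol and SAP*

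**What the plan says.** Section 2.0 (Secondary Objectives, item 1) sets the aim of quantifying necrosis by CT volumetry and correlating it with RECIST response. Section 14.0 repeats that aim and adds correlation with time to progression. The method it then gives for the necrosis–RECIST relation is: "Using 50% necrosis as threshold we plan to evaluate the degree of agreement between RECIST and necrosis response", "using Cohen's kappa and McNemar's test".

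The plan does not reduce necrosis to a binary measure everywhere. Section 4.1 (Measurement of Treatment Response) says that "the volumetric assessment will use a continuous scale of percent tumor necrosis", and Section 14.0 gives a precision for it as a continuous quantity: "percent necrosis can be estimated to within +/- 14% of its standard deviation".

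Section 14.0 gives no reason for the 50% cut, no expected share of patients on either side of it, no target or precision for kappa, and no statement on whether the arms are pooled. Section 2.0 explains why expected rates are missing: "Since there is no historical data on imaging response to treatment for either group". Section 3.0 (Preliminary Data) gives a qualitative reason to expect the two measures to diverge: "RECIST criteria have been found to be insensitive when used to evaluate other tumors that develop significant necrosis in response to treatment".

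**The concern.** Correlation and agreement are different questions. Two measures can be strongly related and still agree poorly as yes/no classifications, simply because one says yes far more often than the other. Kappa penalises that imbalance. McNemar's test looks at nothing but the imbalance.

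The protocol's rationale is that tumors may become necrotic without shrinking. Its example in Section 12.0 (Figure 2) shows tumor volume up 29.5% while the necrosis ratio rose 388.8%. Response is read on a CT taken only 2–3 weeks after the first treatment is complete. RECIST response could therefore be much the rarer of the two.

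Sections 3.0 and 2.0 go on to ask whether necrosis or RECIST response might serve as a surrogate for time to progression or survival. If a low kappa were taken to mean that the two measures are unrelated, when it only reflects unequal frequencies, that discussion would start from a wrong premise.

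**Working it through.** **The plan's own figures.** Section 14.0 states that "With 50 patients in each arm response rates can be estimated to within +/- 14" percent. At the worst case p = 0.5 and 95% confidence (both assumed, since the plan states neither), 1.96 × √(0.25/50) = 0.139, so it reproduces. It concerns each arm's response rate and says nothing about kappa, for which the plan gives no figure. The necrosis precision of 14% of a standard deviation equals 1/√50 = 0.141, which is one standard error and not a 95% half-width (1.96/√50 = 0.277). That is a separate matter.

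**Inputs.** Sample size: "100 patients will be enrolled, 50 in each study arm". The RECIST response rate r and the share q at or above 50% necrosis are not given, so both are assumed over a range. The nearest figure in the documents is a 78% objective response by EASL criteria at 6 months with doxorubicin beads (Section 3.0). That is a different criterion at a different time, and it is used here only as a high value for q.

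**Ceiling of kappa.** The best case for r < q is full nesting, where every RECIST responder is also a necrosis responder. Then:

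- observed agreement: po = 1 − (q − r)
- chance agreement: pe = rq + (1 − r)(1 − q)
- maximum kappa = (po − pe)/(1 − pe)

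Example, r = 10% and q = 50%: po = 1 − 0.40 = 0.60; pe = 0.05 + 0.45 = 0.50; maximum kappa = 0.10/0.50 = 0.20.

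| RECIST response (assumed) | ≥50% necrosis (assumed) | Maximum kappa |
|---|---|---|
| 5% | 40% | 0.15 |
| 5% | 50% | 0.10 |
| 5% | 60% | 0.07 |
| 10% | 50% | 0.20 |
| 10% | 60% | 0.14 |
| 10% | 78% | 0.06 |
| 20% | 60% | 0.29 |
| 10% | 20% | 0.62 |
| 20% | 30% | 0.74 |
| 30% | 50% | 0.60 |
| 30% | 40% | 0.78 |

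The ceiling depends on how far apart the rates are. With 50% of patients above the cut, RECIST response must reach 10%, 20% or 30% before kappa can reach 0.2, 0.4 or 0.6. With 78% above the cut, the corresponding RECIST rates are about 28%, 47% and 60%.

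**What McNemar adds.** Take 100 patients with rates of 10% and 50%, and compare the two extremes:

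- Full nesting: 10 responders on both, 0 on RECIST only, 40 on necrosis only, 50 on neither. Kappa = 0.20. Exact two-sided McNemar p = 2/2^40, about 2 × 10⁻¹².
- No association: 5 on both, 5 on RECIST only, 45 on necrosis only, 45 on neither. Agreement is 0.50, equal to chance, so kappa = 0. Discordant pairs are 5 and 45, and exact p = 2 × (1 + 50 + 1,225 + 19,600 + 230,300 + 2,118,760)/2^50, about 4 × 10⁻⁹.

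McNemar is decisive in both cases, so it cannot separate the strongest possible positive association from none. Kappa can, but here only within a range of 0 to 0.20, which looks poor throughout unless the ceiling is printed beside it.

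**Very few responders.** If RECIST response were 5%, the chance of no responder at all is 0.95^50 = 7.7% in one arm and 0.95^100 = 0.6% in both together. Kappa would then be 0 whatever the necrosis result.

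**The case against.** The strongest reply is that kappa and McNemar suit the question in the sentence that names them, which is about agreement. If one method calls 10% of patients responders and the other 60%, the methods do disagree; a low kappa says so correctly, and McNemar shows that unequal rates are part of the reason. A 2×2 table needs a cut, and using one there does not replace the continuous measure kept in Sections 4.1 and 14.0. The insensitivity cited in Section 3.0 was seen in other tumors, and how necrosis and RECIST relate in hepatocellular cancer is what the study sets out to learn. All of this stands.

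It rules out three stronger readings that a reader might infer:

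- **That kappa is capped near zero whenever RECIST response is the rarer.** The gap must be wide; at 20% versus 30% the ceiling is 0.74.
- **That the plan throws away the continuous scale.** It keeps the scale and states an intention to correlate.
- **That the secondary objective will go unanswered.** Agreement will be answered, and Sections 2.0 and 14.0 also plan to quantify necrosis and relate imaging response to time to progression and survival.

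The reply does not supply a method for the correlation itself. The Kaplan–Meier and log-rank methods in Section 14.0 concern time to progression and survival, and no named analysis sets continuous necrosis against RECIST change.

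**Conclusion.** The point holds as a gap in specification. The objective asks whether necrosis and RECIST response are associated, and the only methods named for that relation measure agreement and equality of rates at one unexplained cut. Its practical size depends on two rates that the documents do not give. Over the assumed values tabulated above, the ceiling on kappa runs from 0.06 to 0.78. It is 0.20 or lower when RECIST response is 10% or less and at least half the patients exceed 50% necrosis. The protocol's rationale makes that plausible; nothing in the documents shows it to be likely.

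The consequence is a risk of misreading one secondary analysis in a trial designed for estimation. The primary endpoint is not touched. This is a low-cost improvement, not a serious flaw.

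**What to change.** In Section 14.0, name the method for the necrosis–RECIST correlation: Spearman correlation of percent necrosis with percent change in the RECIST sum, both from the 2–3 week response CT, with a confidence interval. State whether the arms are pooled.

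Keep the 2×2 table at the 50% cut, with kappa and McNemar, and label it the agreement analysis. Report the full table, both margins, and the maximum attainable kappa beside the observed value.

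An area under the ROC curve for percent necrosis by RECIST response is optional. With few responders (about 5 in 100 at a 5% rate) it would be imprecise and should be presented as such.

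The change uses measurements already planned, needs no extra visits, scans or patients, and costs only a little additional analysis.

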### **Secondary Objectives**

1. Quantify the amount of tumor necrosis before and after initial treatment in both groups by CT volumetry, and correlate with response to treatment by RECIST criteria.
2. Evaluate toxicity, time to progression (TTP) and survival in each treatment arm.  
Determine if initial imaging response to treatment, as manifested by either RECIST criteria or volume of necrosis correlates with either TTP (by RECIST or volumetric method) or survival.

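### Section 14.0 does not say how continuous percent necrosis will be related to TTP and survival; it names only a log-rank test between undefined groups

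*Combined protocol and SAP*

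**What the plan says.** Section 4.1 (Measurement of Treatment Response) sorts patients into RECIST categories but states that "the volumetric assessment will use a continuous scale of percent tumor necrosis".

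The link between necrosis and outcome is a declared aim in several places. Section 2.0 (Secondary Objectives) asks whether RECIST response or "volume of necrosis correlates with either TTP (by RECIST or volumetric method) or survival". Section 3.0 (Preliminary Data) says "These 2 measures of response to treatment will be correlated with TTP and survival", with a view to a surrogate outcome marker.

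Section 14.0 puts two questions into one objective: whether the doxorubicin beads prolong TTP or survival, and "if initial imaging response to treatment, as manifested by necrosis, correlates with either endpoint". For that objective it offers a single sentence of method: "We will use the Kaplan-Meier method to estimate the survival probabilities and we will use the log-rank test to compare groups". The power statement that follows is about the two arms.

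The preceding paragraph of Section 14.0 begins by saying that necrosis will be correlated with RECIST response and with TTP. It then sets a 50% necrosis threshold, but the sentence that does so names only kappa and McNemar's test for agreement with RECIST. No Cox model, other regression or concordance measure appears anywhere in the document.

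**The concern.** A log-rank test compares categories. A continuous predictor can enter it only after being cut, and the plan gives no cut for TTP or survival. Two things follow. Cutting a graded predictor usually lowers the power to see an association. Leaving the cut open also allows it to be chosen once the outcomes are known, which raises the false-positive rate.

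What is at stake is the trial's contribution on necrosis as a surrogate. Section 14.0 says this aim should supply preliminary data for a definitive trial. For that purpose a planner needs a hazard ratio per unit of necrosis with a confidence interval, and a log-rank p-value at an unstated cut does not provide one.

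**Working it through.** **1. The plan's own figure.** The plan gives none for the necrosis-outcome association. Its 80% power at a hazard ratio of 3 concerns the arms and is not used here.

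**2. The two readings of groups.**
- Arms only: the necrosis part of the objective has no method.
- Necrosis groups: the measure is cut, at a point the plan does not state.

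**3. Information lost by one cut.** With a linear log-hazard and a modest effect, the share of information kept by a cut at c is the squared correlation between X and the indicator X > c. With p the share of patients above c:
- Normal X: φ(c)² / [p(1−p)]. Median: 0.3989² / 0.25 = 0.637, so 36% is lost. Split 30:70: 0.576, 42% lost. Quartile: 0.539, 46% lost. Split 20:80: 0.490, 51% lost.
- Uniform X: 3p(1−p). Median: 0.75, 25% lost. Quartile: 0.5625, 44% lost.

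Necrosis is bounded at 0-100% and the documents give no distribution, so Beta shapes were assumed, each cut at 50% necrosis:

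| Assumed shape | Share above 50% | Lost |
|---|---|---|
| U-shaped, Beta(0.5,0.5) | 50% | 19% |
| Uniform | 50% | 25% |
| Beta(2,2) | 50% | 30% |
| Beta(3,1) or Beta(1,3) | 87.5% or 12.5% | 46% |
| Beta(5,2) or Beta(2,5) | 89% or 11% | 55% |

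A still more lopsided shape, Beta(1,4) with 6% above the cut, loses 60%. Ordered groups scored as a trend lose less (normal / uniform): tertiles 21% / 11%, quartiles 14% / 6%, quintiles 10% / 4%.

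**4. What that means for power.** Inputs from Section 14.0: 100 patients, about half dying, so about 50 deaths; Type I error 5% (two-sided assumed).
- Effect detectable with 80% power if necrosis stays continuous: (1.96 + 0.8416) / √50 = 0.396 log hazard per SD, a hazard ratio of about 1.49.
- Power at that effect after a median cut: Φ(2.8016 × √0.637 − 1.96) = 61% if normal; Φ(2.8016 × √0.75 − 1.96) = 68% if uniform.
- Deaths needed after a median cut to match 50 analysed continuously, normal case: 50 / 0.637 = about 79.

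Simulation check (4,000 trials per row, 100 patients, 50 events, log hazard ratio 0.4 per SD):

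| Distribution and cut | Continuous | Cut |
|---|---|---|
| Normal, median | 78% | 58% |
| Uniform, median | 79% | 67% |
| U-shaped, median | 81% | 71% |
| Normal, upper quartile | 78% | 43% |

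The documents give no event count for TTP. The fractional loss in step 3 does not depend on that count.

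**5. Choosing the cut afterwards.** Simulations with no association (100 patients, 2-4 years of follow-up assumed) that take the most favorable of cuts at 25%, 50% and 75% necrosis reject in about 11-17% of trials, depending on the assumed distribution. For scale, three independent 5% tests would give 1 − 0.95³ = 14.3%. Higher values arise where a cut leaves very few patients on one side and the large-sample log-rank test is unreliable. A cut fixed beforehand rejects about 5% of the time, as does the continuous test.

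**The case against.** A reader might infer that the plan forces an arbitrary cut and thereby discards a third or more of the information. The documents do not support that.

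- The word groups is undefined and may mean the arms, since the next sentence of Section 14.0 speaks of the arms. The fault is an unspecified method, not a chosen dichotomy.
- The 50% threshold is the only necrosis-response cut in Section 14.0, and the paragraph containing it also mentions TTP. It could be carried over. The plan does not say that it will be.
- A third or more is the result for a normal predictor with one cut and a linear log-hazard. Flatter or U-shaped distributions lose less, as do several ordered groups. If risk really changes at a threshold near the cut, little is lost.
- Nothing in the plan proposes searching over cuts. The 11-17% describes what an open cut permits, not what the investigators intend.
- Section 14.0 says the trial is not meant to test a hypothesis and calls this aim preliminary.

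All of this stands and limits the point. It does not remove it: under either reading of groups, the plan lacks a stated and adequate method for relating a continuous measure to two censored endpoints.

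**Conclusion.** The point holds as a gap in specification. Section 14.0 commits to relating initial percent necrosis to TTP and survival but supplies only Kaplan-Meier and a log-rank test, with no defined groups, no cut for this purpose and no regression model.

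The cost is conditional. If one cut is used, about 19% to 55% of the information is lost over the main shapes assumed, given a linear log-hazard. These figures rest on assumed distributions, because the documents give none. If the cut is picked from the data among three candidates, the false-positive rate is about 11-17% instead of 5%.

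The point concerns a secondary, preliminary aim. It does not touch the primary response-rate estimates, the comparison of arms or the necrosis-RECIST agreement analysis.

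**What to change.** In Section 14.0, state that percent necrosis after the initial treatment will be related to TTP and to survival by a Cox model with necrosis as a continuous covariate. Report the hazard ratio per 10 percentage points with its 95% confidence interval, and check for non-linearity, for example with a spline. Say that Kaplan-Meier curves by necrosis are for display only, at a cut named in advance; the 50% already in Section 14.0 would serve. State also that the log-rank test compares the two arms, if that is what is meant.

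The cost is a few lines of wording. No new data, scans, visits or patients are needed.
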